By completing specific objective #1, we will be fully prepared for TASKPEN pilot testing, having ready an adapted version of TASKPEN that includes all the essential implementation strategies necessary to overcome barriers to HIV-NCD integration in routine care settings. While the peripheral elements and implementation strategies used to introduce TASKPEN may undergo adaptation under specific objective #1, it is important to note that the 5 core, evidence-based components outlined in Table 1 and proposed for this pilot will not substantively change. Under specific objective #2, we will launch the TASKPEN pilot and fully task-shift our intervention to NPHWs and integrate it within the PEPFAR-supported HIV service delivery platform. Concurrently with implementation, during the pilot we will identify facilitators and barriers to TASKPEN introduction, assess preliminary implementation outcomes and patient and provider preferences related to integrated management of cardio-metabolic complications for PLHIV, ascertain early clinical outcomes for patients before and after TASKPEN piloting, and collect formative costing data.

b. Study design

For this objective, we will conduct a quasiexperimental "mini" cross-sectional stepped-wedge study at the 2 pilot sites employing a mixed methods approach. First, at the two pilot sites (i.e. A and B), we will conduct a baseline assessment of select outcomes for PLHIV receiving the existing standard of care. This will involve conducting a brief biobehavioural survey or "patient survey" among a consecutive sample of ~376 adult PLHIV presenting for routine HIV services at the two sites (i.e., ~188 PLHIV per site, see Sample Size and Statistical Power below). After this first patient survey, one randomly selected facility (i.e. cluster) will be switched to the full TASKPEN intervention. The patient survey will be repeated again with another ~376 adult PLHIV after ~3 months at both sites before switching the second site to the full TASKPEN intervention. After switching the second

Figure: Study schematic with "mini" stepped wedge and nested cohort.

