Nested cohort participants will be the only study participants having more than one encounter with the study team. As such, we will schedule study follow-up visits approximately every 3 months over a ~9-month period starting at 2 weeks from the time of the baseline patient survey. Thus, their total engagement with the study will amount to about 4 follow-up visits (at ~2 weeks and then around 3 and 6 months from the baseline survey plus one study exit visit at around 9 months). Study visits will be largely aligned with the schedule of routine clinic visits stipulated in the Zambia national HIV guidelines (i.e., every 3-6 months for established ART patients and more frequently during the first month of treatment for new ART patients) and will be scheduled mostly for times when the study teams are conducting the midline and endline surveys at the study sites. Study research assistants, who are not

providing any interventions as part of TASKPEN, will contact the participants in the nested cohort via phone call every month to check vital and clinic status (still in care at original site) and ascertain any changes in household location. If the participant is unreachable, community tracing will be done to verify whereabouts leveraging existing CIDRZ community tracing platforms in Lusaka. At the next time a survey assessment is done at the site, and before the clinic is switched from control to intervention, the nested cohort participants will be re-assessed by the team.

Study follow-up procedures will be designed so as not to disrupt routine care delivery and will include: determination of retention in integrated HIV/NCD care and referral for routinely available adherence and psychosocial counselling and back-to-care services, as appropriate; lab monitoring for cardio-metabolic NCDs (see laboratory procedures below) if not already done by the government health workers during their routine health visits; brief survey administration to assess adherence, nutritional status, tobacco and alcohol use, and other NCD-related health parameters; and completion of the quality of life and DCE questionnaires.

e. Data collection plan and tools

Data collection overview

As in specific objective #1, data collection activities for specific objective #2 will involve a combination of NHSR and implementation research activities detailed below.

ii. Non-human subjects research activities

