At both sites, during a ~1-month "run in period," we will establish basic study infrastructure to enable quantitative data collection during the patient surveys. This will involve fully equipping study offices at the sites and ensuring information technology connectivity and available computer hardware. Then, study staff will begin data collection on cardio-metabolic and implementation outcomes of interest using three cross-sectional patient surveys. The first two surveys (at baseline [0 months] and midline [3 months] will be done immediately prior to a site switching to the intervention; a final survey will be done at 6 months and serve as the "endline" assessment. The surveys will ask questions about participant socio-demographics, HIV and cardio-metabolic NCD history, and health behaviours. It will involve trained study staff administering a tablet-based questionnaire to participants, as well as taking participants' anthropomorphic measurements (e.g., height, weight, and waste circumference), vital signs (e.g., pulse and blood pressure), and a small blood sample to measure random/ fasting blood glucose, haemoglobin A1c, cholesterol levels, and other biomarkers. These laboratory tests will follow MOH recommendations and may include new point-of-care diagnostic technologies (see laboratory procedures section), and the results will be reported to patients and the clinic for clinical management. Any participant found to have newly diagnosed hypertension, diabetes/ pre-diabetes, and/or dyslipidaemia will be linked to care at the study sites. In addition, the study QA/QC nurse and study clinical scientist/ doctor will be available to act immediately on any vital sign or laboratory abnormality, including to offer patient counselling, provide warm "handoffs" to clinical staff, refer patients for acute care at the study sites, and prescribe appropriate outpatient treatment for non-acute issues in cases where MOH staff are not available (e.g., after business hours). Finally, we will ask participants to provide a phone number so we can invite those identified with hypertension, diabetes/ pre-diabetes, and/or dyslipidaemia through the survey to be followed in the nested cohort.

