The primary measures for the pilot are adoption, acceptability, feasibility, appropriateness, as well as the preliminary effect of the TASKPEN intervention. We will assess implementation outcomes principally using a handful of theoretical frameworks. A brief questionnaire will be administered that will feature the simple 12-item implementation survey (incorporating empirically supported measures for acceptability, feasibility, and appropriateness) mentioned above, among other implementation-relevant items⁹⁸. We will further examine **acceptability** in our qualitative data as a construct comprising multiple dimensions⁹⁹. We will include open-ended questions guided by established implementation science frameworks such as the CFIR to elaborate on what makes the intervention appropriate or not and acceptable or not. We will further evaluate **feasibility** in our qualitative data by applying the theoretical basis of "compatibility" from Rogers' "Diffusion of Innovation" theory, among other theories¹⁰⁰.

We will describe implementation outcomes of **adoption** and **reach** according to RE-AIM. We will also calculate **retention** as the proportion of participants enrolled in the nested cohort and considered to be engaged in care at ~6 months. We will measure **adherence** in the nested cohort by reviewing pharmacy records at ~6 months to determine consistent access to anti-hypertensive, diabetes, and dyslipidaemia medications, as appropriate, as well as antiretroviral therapy. For the patient surveys, we will ask participants about adherence and review pharmacy records to examine medication adherence overall at the study sites.

Finally, we will pilot the feasibility, applicability, and completeness of the following measures in the cross-sectional assessments and nested cohort for adoption in the future follow-on trial:

- 1. **Dual** HIV and NCD disease control, defined as:
 - a. HIV RNA level of <200 copies per milliliter on the most recent measure; **AND**

- The absence of the following NCD conditions as defined by the nested cohort eligibility criteria:
 1) uncontrolled systolic hypertension;
 2) uncontrolled diabetes mellitus;
 and
 3) uncontrolled dyslipidaemia.
- 2. 10-year ASCVD risk score (based on American College of Cardiology/ American Heart Society guidelines)
- 3. The HIV-specific *D.A.D. CVD risk score*: (The Data-collection on Adverse Effects of Anti-HIV Drugs) score.
- 4. Quality of life as measured by WHOQOL-HIV-BREF ¹⁰¹.

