Using baseline, midline, and endline patient survey data and routine EMR data, we will assess the implementation outcomes described in Table 6. We will calculate standardized scores for validated instruments in our implementation survey. Comparisons of proportions for the aforementioned implementation outcomes will be done by calculating prevalence ratios and associated 95% confidence intervals as appropriate. Comparisons of continuous outcomes will be done by the Z-test/ 2-sample T-test or the Wilcoxon Rank-Sum test as appropriate.

To understand patient-level outcome measures of **disease control, retention**, **adherence**, and **viral suppression**, we will analyse data from the patient surveys. We will estimate **dual disease control** as the proportion of participants in the intervention and control periods who have a HIV viral load <200 copies/ml and do not have uncontrolled systolic hypertension, diabetes, and/or dyslipidaemia. We will calculate **retention** as the proportion of participants considered to be consistently engaged in care at 6 months according to the national HIV treatment program definition (e.g., without evidence of death, default, or loss to follow up defined as ≥30 days having elapsed since a missed pharmacy refill/ clinic visit). We will measure **adherence** in the nested cohort by reviewing pharmacy records at 6 months to calculate the medication possession ratio (MPR) over that time frame for anti-hypertensive, diabetes, and dyslipidaemia medications, as well as antiretroviral therapy. We will calculate **viral suppression** as the proportion of survey participants meeting established thresholds of suppression (e.g., viral load <1,000 copies/ml or <200 copies/ml) at 6 months following ART initiation and/or study enrolment. To compare outcome measures, we will report differences and ratios with accompanying 95% confidence intervals. We will compute variance for differences and ratios using the sandwich variance estimator or appropriate resampling approaches to account for the clustered nature of the data by site.

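### The cohort's single 6-month medication possession ratio straddles the second site's switch, so it mixes control and intervention time and cannot give a before-and-after comparison

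*Combined protocol and SAP*

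**What the plan says.** All references are to Specific Objective #2 of the combined protocol and SAP.

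- **Measure.** Section g. Data analysis, i. Quantitative data analysis, obtains cohort adherence by "reviewing pharmacy records at 6 months to calculate the medication possession ratio (MPR) over that time frame", for antihypertensive, diabetes and lipid drugs and for antiretroviral therapy. Section e, vii. Outcomes, gives the same time point: "reviewing pharmacy records at ~6 months to determine consistent access to anti-hypertensive, diabetes, and dyslipidaemia medications".
- **Switch dates.** Section b. Study design says: "After this first patient survey, one randomly selected facility (i.e. cluster) will be switched to the full TASKPEN intervention". The survey is repeated "after ~3 months at both sites before switching the second site to the full TASKPEN intervention". Section e, iii. Quantitative research data collection, puts the surveys at 0, 3 and 6 months, the first two just before a switch.
- **Cohort clock.** Section d, vii. Nested cohort follow-up procedures, counts visits from the baseline survey: "at ~2 weeks and then around 3 and 6 months from the baseline survey plus one study exit visit at around 9 months".
- **Purpose of the cohort.** Section b expects finer comparisons both between sites and within each site. Section a. Overview speaks of early clinical outcomes before and after the pilot begins.
- **Planned reporting.** Section g, i promises differences and ratios with 95% confidence intervals for the outcomes it lists. It names control and intervention periods for dual disease control, and names no contrast for adherence.
- **Other adherence data.** For the patient surveys, section e, vii adds: "we will ask participants about adherence and review pharmacy records to examine medication adherence overall at the study sites". Sections d, vii and e, iii also collect adherence from cohort members by questionnaire.

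**The concern.** The possession ratio is accumulated over time, so its meaning depends on what happened during the window. An undivided window from baseline to month 6 contains the second site's switch. That site's value is then neither a control value nor an intervention value, and the first site's value is intervention throughout. No split at the switch and no pre-baseline ratio is planned.

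Each cohort member thus has one ratio per drug class, with nothing to compare it with in the same person or at the same site. The only contrast left for this ratio is site against site. That contrast carries a reduced difference in exposure and cannot be separated from other differences between two facilities. This matters because the pilot is meant to inform the planning of a larger trial.

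**Working it through.** **The plan's own figure.** The documents give no size, power, mean or standard deviation for the possession ratio. Their only power figure is 80% for dual HIV/NCD control in the surveys (section d, v). It reproduces with the Hussey-Hughes variance for 2 clusters and 3 periods, total variance 0.6 × 0.4 = 0.24, and ICC 0.25:

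- between-cluster variance 0.24 × 0.25 = 0.06; within-cluster variance 0.18; 0.18/188 = 0.000957 per cell;
- Var = 2 × 0.000957 × (0.000957 + 3 × 0.06) / (1 × 0.000957 + 2 × 0.06) = 0.002865, so SE = 0.0535;
- power = Φ(0.15/0.0535 − 1.96) = 0.800.

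Other choices of variance give 0.68 to 0.89. This calculation does not use the possession ratio, so the present point leaves it alone.

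**Exposure in the 6-month window.** Let c be the mean ratio under usual care and d a constant additive effect.

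- First site, switch at month 0: share 6/6, expected ratio c + d.
- Second site, switch at month 3: share 3/6, expected ratio c + 0.5d.
- Difference: (1 − 0.5)d = 0.50d, plus any site difference.

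With assumed c = 0.60 and d = 0.10, the true difference of 0.10 appears as 0.05, and the true ratio 0.70/0.60 = 1.167 appears as 0.70/0.65 = 1.077.

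**Sensitivity to the shape of the effect** (difference between sites as a share of the full effect d):

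| Assumption | Undivided, months 0-6 | Split, months 0-3 |
|---|---|---|
| Constant effect | 0.50 | 1.00 |
| 1-month lag | 0.50 | 0.67 |
| 2-month lag | 0.50 | 0.33 |
| 3-month ramp | 0.50 | 0.50 |
| 6-month ramp | 0.375 | 0.25 |
| Waning to half by month 6 | 0.31 | 0.875 |

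Delaying both switches by 0.5 or 1 month leaves the undivided figure at 0.50. Starting a 6-month window at the 2-week visit gives 0.42 for a constant effect. No full 6-month window exceeds 0.50. A shortened window of months 0.5 to 6 reaches about 0.54 with a lag or a 3-month ramp, which is a trivial exception.

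**Another reading of 6 months.** If the window meant six months after each site's own switch (months 3 to 9 at the second site), both sites would be wholly intervention and the ratio would have no control time. The visit schedule is counted from the baseline survey, which favours the first reading.

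**Illustration of precision** (assumed SD 0.25, d = 0.10, 100 per site, clustering ignored). Power = Φ(d/(SD × √(2/100)) − 1.96). The full contrast gives Φ(2.83 − 1.96) = 81% and the halved contrast Φ(1.41 − 1.96) = 29%. Over SD 0.20 to 0.30 the figures are 94% to 65% against 42% to 22%. No such test is planned. A 3-month ratio may also have a larger SD than a 6-month one, so the comparison flatters the split.

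**The case against.** The strongest reply is that adherence does not rest on this ratio alone. Survey participants are asked about adherence and their pharmacy records are reviewed. Cohort members also complete the midline and endline surveys and answer adherence questions at follow-up visits. Adherence is therefore collected at about 0, 3 and 6 months at both sites, and the baseline survey precedes the first switch. A reader might infer that any effect on adherence is at best halved, or that the first site has no control value for adherence at all. The documents do not support either reading: both hold for the possession ratio only. The survey source has its own gap, since no metric, window or period split is defined for it.

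A reader might also infer that the plan compares the possession ratio between control and intervention periods. It does not say so; the site-against-site contrast is what the measure would permit, not an analysis the plan states.

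Third, the cohort is for feasibility and has no a priori hypothesis test. A 6-month ratio is usable as a plain description of access to medicines. That stands, and it limits the weight of the point. It does not answer the expectation of within-site comparisons, which one value per person cannot meet.

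Finally, the remedy has limits. The months 0-3 contrast is still one site against one site. Table 4 shows how far the two tentative sites differ: 80% against 0.4% in what appears to be the blood-pressure column. A pre-baseline window would need more hand abstraction and is undefined for members not yet on NCD drugs. These limits stand and shape the fix.

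**Conclusion.** The concern holds for the cohort possession ratio. As defined, it is about 100% intervention time at the first site and about 50% at the second, and it gives no before-and-after value at either. If the sites are compared directly, a constant effect appears at about half its size and is fully confounded with site. The share is about 0.31 to 0.375 if the effect wanes or builds slowly over 6 months. These figures assume switches about 3 months apart, a window starting at baseline and an unadjusted comparison; the documents give no mean, SD or effect for the ratio.

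This is a secondary measure with an unspecified contrast, and the powered survey endpoint is untouched. The change is still worth making, because a better measure can be had from records the study already abstracts.

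**What to change.** Using dispensing dates in the cohort records already being abstracted:

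1. Compute the ratio per drug class for months 0-3 and 3-6 (and 6-9 if wanted), split at each site's actual switch date, and label each window control or intervention.
2. Carry days' supply across window boundaries, so that a refill collected before the switch is credited to the days it covers.
3. Report the second site's within-person change from control to intervention, for members with a defined ratio in both windows. State that it also contains any calendar trend.
4. Report the months 0-3 between-site contrast, stating that it remains one site against one site and reflects only the first three months of exposure. With a lag or ramp it need not exceed the 6-month figure; its gain is that neither site's window mixes the two conditions.
5. Add a pre-baseline window only for antiretrovirals and for members already on NCD drugs, where records allow. Use the baseline survey adherence data for the first site's control value, and define their metric.
6. Keep the 6-month ratio, if wanted, as a description of overall access.

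The split itself costs programming and a few lines of analysis text. The ratio becomes coarser if refills follow routine visits every 3 to 6 months. Any pre-baseline window needs some further chart abstraction.

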site, both pilot sites A and B will implement the full TASKPEN intervention for another ~3 months after which time a third and final "end line" patient survey will be conducted. Survey data will be used to estimate the pilot effect size of the TASKPEN intervention to aid in planning a future larger trial and to measure WHO PEN process indicators for all PLHIV in care who accessed routine health services during the pilot period.

Complementing the baseline, midline, and endline patient surveys will be a "nested cohort" of PLHIV with cardio-metabolic comorbidities enrolled at both sites beginning at baseline. At each site, we will enrol a subset of ~100 baseline survey participants (i.e., ~200 total) found to have at least one cardio-metabolic complication or risk factor (see below) on the baseline survey. We will then follow these nested cohort participants longitudinally for ~9 months at site A and site B. A nested cohort sample size

TASKPEN Study

of 200 PLHIV was selected to represent about 50% of all baseline survey participants who are estimated to have a cardiometabolic co-morbidity at each site (i.e., ~188 PLHIV in care per site who complete a baseline survey x ~50% of survey participants with hypertension, diabetes, and/or dyslipidaemia = ~100 participants per site), consistent with estimates for the prevalence of cardiometabolic comorbidities among PLHIV in Lusaka, Zambia. Moreover, the nested cohort sample size of ~200 total participants (~100 per site) is intended to assess the feasibility of the intervention and longitudinal follow up of study participants to inform a future larger trial; it is not intended to test a hypothesis *a priori*. By enrolling a nested cohort, we can use their data to enrich inferences made from the cross-sectional surveys and will be able to make more granular comparisons between and within sites (i.e. with an external and internal comparator group, respectively).

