For the cross-sectional patient surveys, we will survey a consecutive sample of 188 eligible patients in care at each clinic at each of the 3-time points (i.e., baseline, midline, and end-line) using a stepped-wedge cluster-randomized design. Applying this design with a sample of 2 clusters (i.e., sites), 3 survey time points, 2 steps, 1 cluster switching from control to intervention at each step, and an average of 564 subjects per cluster (i.e., 188 participants per cluster per period) achieves 80% power to detect a risk ratio of 1.25 (for the risk of dual HIV/NCD control during the intervention period compared to the control period) at the 0.05 significance level with an inter-class correlation coefficient of 0.25. We assumed that

the proportion of participants achieving dual HIV/NCD control is 0.75 under the alternative hypothesis, and 0.6 under the null hypothesis, and used the two-sided Wald Z-Test as the test statistic. Based on the above calculation, we will survey 564 eligible patients at each clinic across the 3-time points (i.e., 3*188=564 eligible patients) to achieve **a total sample size of 1128 participants** for the mini stepped-wedge. It is important to note that participants previously surveyed will not be eligible for subsequent surveys—i.e., once interviewed, a patient should not be eligible for interview in subsequent surveys unless they are part of the nestd cohort. Finally, as part of the baseline, midline, and endline cross-sectional surveys, we will review de-identified routine data for all PLHIV in care at the study sites during the study period to estimate HIV viral load completeness, NCD-variable data completeness (e.g., routine weight and blood pressure measurements), and performance on WHO PEN indicators in the routine medical record.

For the nested cohort component, the total sample size of ~200 participants was selected for operational feasibility and to assess our ability to collect longitudinal cardio-metabolic data, but does not involve *a priori* hypothesis testing.

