For qualitative data, final qualitative transcripts will be reviewed for accuracy against original notes and recordings, for at least 5% of the transcripts. Any errors will be corrected by the person who conducted the interview using good clinical practice (GCP) correction procedures. Monitoring visits will be conducted on an ad hoc basis to ensure that data collection is being done well. Any retraining will be done on-site on an as-needed basis, to ensure that collected data are of high quality.

iv. Data ownership, sharing and governance

All study data will be owned by the Zambia Ministry of Health (MOH) as the stewards of the national HIV program. As the owners of the data, the Zambia MOH will ultimately be responsible for oversight of all data governance issues. Qualitative data will not be shared due to the small sample size involved and the potential for deduction. All decisions regarding data dissemination, for example at the request of a journal at the time of publication, will be made by the Zambia MOH as the owners of the data.

g. Data analysis

i. Quantitative data analysis

We will summarize background characteristics (for participants and facility) by the intervention periods (control, intervention). The preliminary effect of the TASKPEN intervention will be estimated by comparisons of the percentage of participants in the patient surveys with dual HIV/NCD control during the control period and the intervention period. We will also calculate CVD risk score based on the ASCVD, D.A.D, or similar and compare this outcome between the control and intervention periods. Binary outcomes will be analysed using generalized linear mixed logistic model with margins to estimate risk ratio and risk difference adjusted for key potential confounders. Health facilities will be specified as random effects while time will be specified as fixed effect in the model. Continuous outcomes will be analysed using linear models to estimate mean score difference in an analogous way.

Quality of life score will be analysed in a similar way. P-values less than 0.05 will be considered statistically significant. We do not plan to impute missing values. All analyses will be performed using Stata 16 MP4 (StataCorp, College Station, TX, USA).

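### With only two sites, confidence intervals from a site-clustered sandwich or site resampling are invalid, and with period terms they collapse to almost zero width

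*Combined protocol and SAP*

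**What the plan says.** All references are to the combined protocol and SAP, section 8, Specific Objective #2.

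- **g. Data analysis, i. Quantitative data analysis, on intervals:** "To compare outcome measures, we will report differences and ratios with accompanying 95% confidence intervals". The variance of these differences and ratios comes from the "sandwich variance estimator or appropriate resampling approaches to account for the clustered nature of the data by site".
- **Same section, on the model for binary outcomes** (a mixed logistic model with margins, adjusted for potential confounders): "Health facilities will be specified as random effects while time will be specified as fixed effect in the model". It adds: "P-values less than 0.05 will be considered statistically significant". It does not say which standard error produces those p-values.
- **d.v, Site sampling and randomization, including sample size and statistical power:** the design has "2 clusters (i.e., sites), 3 survey time points, 2 steps", one site switching at each step, 188 participants per site per survey, and an "inter-class correlation coefficient of 0.25". The power calculation "used the two-sided Wald Z-Test as the test statistic".
- **b. Study design:** "Survey data will be used to estimate the pilot effect size of the TASKPEN intervention to aid in planning a future larger trial".

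The quantitative analysis text gives no small-sample correction, no t reference distribution and no alternative for a design with two clusters.

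**The concern.** A sandwich estimator clustered by site learns the variance from how the site-level score totals scatter around zero. With two sites there are two totals, and the fitted model forces them to cancel. Once period is in the model, almost nothing is left from which to estimate the variance of the treatment effect. Resampling whole sites has the same problem.

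The software will usually still print a standard error, so nothing warns the analyst that it is meaningless. The plan would then report an effect of TASKPEN on dual HIV/NCD control with a very narrow interval, although the data support only a wide one. The follow-on trial would be sized on that false precision.

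**Working it through.** **1. The plan's own power figure.** Inputs from d.v: 2 sites, 3 surveys, 188 per cell, 0.60 against 0.75, ICC 0.25, two-sided 0.05, Wald Z. Total variance is 0.6 × 0.4 = 0.24, so the between-site part is τ² = 0.06 and the residual per cell is σ² = 0.18/188 = 0.000957. In the Hussey–Hughes formula with treatment pattern (0,1,1) and (0,0,1):

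Var = 2σ²(σ² + 3τ²) / (σ² + 2τ²) = 2 × 0.000957 × 0.18096 / 0.12096 = 0.002865, so SE = 0.0535.

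Power = Φ(0.15/0.0535 − 1.96) = 0.80. The stated 80% is reproduced. It uses a model-based variance; the site-clustered sandwich plays no part in it.

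**2. The sandwich with period terms (linear case, equal cells, no covariates).** Let A be the first site to switch and B the second, with survey means A1–A3 and B1–B3.

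- *Site and period terms.* The effect is (A2 − B2) − [(A1 − B1) + (A3 − B3)]/2. The weights are (−0.5, 1, −0.5) at A and the reverse at B. One residual degree of freedom remains, so the residual cell means must be (r, 0, −r) at A and (−r, 0, r) at B. Site A contributes −0.5r + 0 + 0.5r = 0, and site B likewise. The clustered variance is 0.
- *Period terms only.* The effect is A2 − B2. The midline cells are fitted exactly, so both contributions are again 0.

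In one worked data set, the logistic model with site and period terms gave a clustered SE of 0.004 for the log odds ratio, against a model-based 0.30.

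**3. Site bootstrap.** There are four equally likely draws. AA and BB make treatment collinear with period (design rank 3 of 4), so the effect cannot be estimated. AB and BA return the original estimate. The bootstrap variance is undefined or zero.

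**4. Simulation with no effect.** 2 sites × 3 surveys × 188, dual control 0.60. Site SDs were 0.1 and 0.5 logits (assumed) and 1.05 logits, which is the ICC of 0.25 put on the logit scale: √(0.25/0.75 × π²/3) = 1.05. Site-by-period SDs were 0, 0.1 and 0.2 logits (assumed). The clustered variance was multiplied by G/(G−1) = 2. The reference is z, as in d.v, unless stated.

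| Analysis | Nominal 95% intervals excluding no effect |
|---|---|
| Logistic, period terms, site-clustered | 96–99.6% |
| Logistic, site and period terms, site-clustered | 98.6–99.7% |
| Mixed logistic, site-clustered: odds ratio and risk difference | 93–98% |
| Mixed logistic, site-clustered: risk ratio | 81–97% |
| Crude, no period terms, site-clustered, z | 32–72% |
| Crude, no period terms, site-clustered, t on 1 df | 6–21% |
| Mixed logistic, model-based SE, no site-by-period variation | 4–9% |
| Facility and period fixed, model-based SE: site-by-period SD 0 / 0.1 / 0.2 | 4–6% / 9–11% / 20–26% |
| Participants resampled within cells: SD 0 / 0.1 / 0.2 | 6–7% / 9–12% / 22% |

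In the second row the median SE of the log odds ratio was 0.0001–0.002, against a true SD of 0.26–0.46. At site SD 1.05, with margins evaluated at a zero random effect, the mixed-model figures were 87% (difference) and 70% (ratio).

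**5. Width of the interval.** At site SD 1.05, the site-clustered interval for the mixed-model risk difference had a median half-width of about 0.6 percentage points. Conditional on the two sites it was about 11–12 points. Analytically, the squared weights sum to 3, so SE = √(3 × 0.24/188) = 0.062 and the half-width is 1.96 × 0.062 = 12.1 points.

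**The case against.** **Period terms are not named beside the variance sentence.** They appear with the mixed model, so the intervals might be crude comparisons of control and intervention periods. That is a fair reading, and the near-zero variance does not apply to it. The z-based crude interval still fails in 32–72% of null runs. A t reference on 1 df brings this to 6–21%, but the plan does not specify one.

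**Resampling is left open.** It could mean resampling participants within site-by-survey cells, which works. But the stated purpose is to account for clustering by site, and within-cell resampling does not do that.

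**The plan adjusts for confounders.** Covariates break the exact cancellation. With three assumed covariates, false exclusion ranged from 76% to 99.5% across the covariate sets and models tried. The collapse is softened, not cured.

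**The ICC scale.** A site SD of 1.05 logits corresponds to an ICC of only about 0.18 on the proportion scale. Applying 0.25 on the proportion scale leaves a residual variance of 0.18: SE = √(3 × 0.18/188) = 0.0536, half-width 10.5 points. The comparison with 0.6 points hardly changes.

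**The mixed model has its own standard errors.** They are acceptable when there is no site-by-period variation (4–9%), and the p-values are affected only if they use the site-clustered variances.

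**This is a formative pilot.** Its primary measures are largely implementation outcomes, and no go/no-go rule depends on these intervals. That limits the consequences, but the surveys are explicitly meant to supply an effect size for the larger trial.

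**Conclusion.** The concern holds. Two sites cannot support a site-clustered sandwich or a site bootstrap, and the plan prescribes that kind of variance without a correction or fallback. With period terms and no covariates, nearly every nominal 95% interval excludes no effect when there is none. With covariates, or in a crude z-based comparison, the intervals are less extreme but still invalid.

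The zero is exact only in the linear model with equal cells and no covariates; in logistic models it is approximate. The percentages rest on the assumed site and site-by-period SDs and on the z reference taken from the power calculation. The point estimate is not affected.

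**What to change.** In g.i, Quantitative data analysis:

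1. Delete the site-clustered sandwich and any resampling of whole sites.
2. Estimate the effect with facility and period as fixed effects, using model-based binomial standard errors or resampling participants within each site-by-survey cell. Keeping the random facility effect with model-based standard errors would also remove the main fault; fixed facility effects are a modest further gain (4–6% against 4–9% false rejection).
3. State that the p-values use the same standard errors as the intervals.
4. State that the intervals are conditional on these two sites and carry no between-site or site-by-period uncertainty. Give the size of that limit: false rejection of about 5% with no site-by-period variation, about 10% at an assumed SD of 0.1 logits and 20–26% at 0.2. The results should be read as descriptive, for planning the larger trial.

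The change costs wording only; no data, sites or visits are added. The reported interval becomes about ±11–12 points (10.5 with the ICC on the proportion scale) against a planned effect of 15 points. Simulated power of the proposed analysis is about 61–72%. The gap from the stated 80% comes from the variance: Φ(0.15/0.062 − 1.96) is about 0.68 with the full 0.24, and about 0.80 with the 0.18 left after an ICC of 0.25 on the proportion scale. Inference does not extend beyond the two sites.
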